10.4.2.3 Safety Analyses

10.4.2.3.1 Analyses of Primary Safety Endpoint(s)

All safety analyses will be performed for the DBTP and the OLTP separately. For safety endpoints in the DBTP, all randomized subjects who received at least 1 dose of investigational product (ie, SAS) will be analyzed according to the randomized treatment unless a subject has received the incorrect dose during the entire DBTP.

10.4.2.3.2 Adverse Events

Subject incidence or exposure-adjusted subject incidence rates of all treatment-emergent adverse events will be tabulated by system organ class and preferred term. Tables of fatal adverse events, serious adverse events, adverse device effects, adverse events leading to withdrawal from investigational product, treatment-related adverse events and significant treatment emergent adverse events will also be provided.

Approved

10.4.2.3.3 Laboratory Test Results

Not applicable, laboratory measurements are only to be performed at screening.

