2.2 Schedule of Activities

Table 2-1. Schedule of Activities - Study Visits Through Double-blind Treatment Period

PROCEDURE	Screening Period		Treatment Period							Notes
	Initial Screening Period	Baseline Period ^a	Double-blind Treatment Period (24 Weeks)							
	(up to 3 weeks before Baseline)	(4 weeks before Day 1)	Day 1 ^b	Wk 4	Wk 8	Wk 12	Wk 16	Wk 20	Wk 24/ ET ^c	
Clinic Visit	X	X	X	X	X	X	X	X	X	
Informed consent	X									
IRT call	X		X	X	X	X	X	X	X	
Part 1 inclusion and exclusion criteria	X									
Demographics	X									
Physical examination	X								X	
Physical measurements	X		X							
Medical history	X									
Neurological medical history	X									
Cardiovascular medical history	X									
Cardiac risk factors	X									
Headache and migraine frequency history	X									
Migraine prevention medication history	X									
Vital signs	X		X	X	X	X	X	X	X	Pre-randomization on Day 1; BP, HR, RR, and temperature

Approved

Footnotes after last page of table.

Table 2-1. Schedule of Activities - Study Visits Through Double-blind Treatment Period

PROCEDURE	Screening Period		Treatment Period							Notes
	Initial Screening Period (up to 3 weeks before Baseline)	Baseline Period ^a (4 weeks before Day 1)	Double-blind Treatment Period (24 Weeks)							
			Day 1 ^b	Wk 4	Wk 8	Wk 12	Wk 16	Wk 20	Wk 24/ ET ^c	
Electrocardiogram	X									
Part 2 inclusion and exclusion criteria			X							Pre-randomization on Day 1
Randomization			X							
Adverse events			X	X	X	X	X	X	X	Post-randomization on Day 1
Serious adverse events	X	X	X	X	X	X	X	X	X	
Adverse device effects ^d			X	X	X	X	X	X	X	
Product complaints			X	X	X	X	X	X	X	
Concomitant therapies review	X		X	X	X	X	X	X	X	
LABORATORY ASSESSMENTS^e										
Urine pregnancy test (females of childbearing potential only) ^f	X		X	X	X	X	X	X	X	A highly sensitive test at screening and at Day 1 pre-randomization of initiation of investigational product
Urine drug testing	X	X	X	X	X	X	X	X	X	Post-randomization on Day 1; Central laboratory
Hematology	X	X (to be performed at the discretion of the investigator)							Central laboratory After screening, hematology testing will be at the discretion of the investigator	

Approved

Footnotes after last page of table.

Table 2-1. Schedule of Activities - Study Visits Through Double-blind Treatment

PROCEDURE	Screening Period		Treatment Period							Notes
	Initial Screening Period	Baseline Period ^a	Double-blind Treatment Period (24 Weeks)							

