	(up to 3 weeks before Baseline)	(4 weeks before Day 1)	Day 1 ^b	Wk 4	Wk 8	Wk 12	Wk 16	Wk 20	Wk 24/ET ^c	
Chemistry	X	X (to be performed at the discretion of the investigator)							Central laboratory After screening, chemistry testing will be at the discretion of the investigator	
HIV, Hepatitis B and C screening	X									Central laboratory
BIOMARKER DEVELOPMENT										
Blood sample			X			X			X	
PHARMACOGENETIC ASSESSMENTS										
Pharmacogenetic sampling (optional) ⁹			X							Post-randomization on Day 1; central laboratory
STUDY TREATMENT										
Amgen investigational product			X	X	X	X	X	X		Pre-filled syringes
CLINICAL OUTCOME ASSESSMENTS/PATIENT-REPORTED OUTCOMES										
Assign eDiary to subject		X								
Subject brings eDiary to center for use during visit or to return			X	X	X	X	X	X	X	Sites retain eDiary at week 24/ET visit
eDiary			X (Daily)							Daily
MPFID			X (Daily)							Daily
HIT-6			X	X	X	X	X	X	X	Post-randomization on Day 1; eDiary in clinic
MFIQ			X	X	X	X	X	X	X	Post-randomization on Day 1; eDiary in clinic
ASC-12			X			X			X	Post-randomization on Day 1; eDiary in clinic

Approved

Table 2-1. Schedule of Activities - Study Visits Through Double-blind Treatment

PROCEDURE	Screening Period		Treatment Period							Notes
	Initial Screening Period	Baseline Period ^a	Double-blind Treatment Period (24 Weeks)							
	(up to 3 weeks before Baseline)	(4 weeks before Day 1)	Day 1 ^b	Wk 4	Wk 8	Wk 12	Wk 16	Wk 20	Wk 24/ET ^c	
MIDAS			X			X			X	Post-randomization on Day 1; eDiary in clinic
BDI-II ^h	X	X ⁱ				X			X	eDiary; in clinic
GAD-7			X			X			X	Post-randomization on Day 1; eDiary in clinic
Sleep Questionnaire			X			X			X	Post-randomization on Day 1; eDiary in clinic
PGIC									X	eDiary in clinic
HRU Questionnaire ^j			X						X	Post randomization on Day 1; in clinic

Page 4 of 4

ASC-12 = Allodynia Symptoms Checklist-12; BDI-II = Beck Depression Inventory-II; BP = blood pressure; DBTP = double-blind treatment period; eDiary = electronic diary; ET = early termination; GAD-7 = Generalized Anxiety Disorder 7-item Scale; HIT-6 = Headache Impact Test-6; HIV = human immunodeficiency virus; HR = heart rate; HRU = Health Resource Utilization; **IRT = Interactive Response Technology**; MFIQ = Migraine Functional Impact Questionnaire; MIDAS = Migraine Disability Assessment; MPFID = Migraine Physical Function Impact Diary; OLTP = open-label treatment period; PGIC = Patient Global Impression of Change; RR = respiratory rate

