Product complaints	X	X	X	X	X	X	X	X	
Concomitant therapies review	X	X	X	X	X	X	X	X	

Footnotes after last page of table.

Approved

Table 2-2. Schedule of Activities - Study Visits Through Open-label Treatment Period

	Treatment Period								
	Open-label Treatment Period (28 Weeks)								
PROCEDURE	Wk 24 (OLTP Entry Visit)	Wk 28	Wk 32	Wk 36	Wk 40	Wk 44	Wk 48	Wk 52/ EOS ^a	Notes
LABORATORY ASSESSMENTS									
Urine pregnancy test (females of childbearing potential only) ^d	X	X			X			X	
Urine drug test	X (to be performed at the discretion of the investigator)								
Chemistry	X (to be performed at the discretion of the investigator)							X	
CLINICAL OUTCOME ASSESSMENTS/PATIENT-REPORTED OUTCOMES									
Site re-assigns eDiary to subject					X				
eDiary					X (Daily)				Daily during assessment study months
Subject brings eDiary to center for use during visit or to return								X	Sites should retain eDiary at EOS visit
MPFID					X (Daily)				Daily during assessment study months
HIT-6								X	eDiary in clinic
MFIQ								X	eDiary in clinic
MIDAS								X	eDiary in clinic

Footnotes after last page of table.

Approved

Table 2-2. Schedule of Activities - Study Visits Through Open-label Treatment Period

	Treatment Period								
	Open-label Treatment Period (28 Weeks)								
PROCEDURE	Wk 24 (OLTP Entry Visit)	Wk 28	Wk 32	Wk 36	Wk 40	Wk 44	Wk48	Wk 52/ EOS ^a	Notes
STUDY TREATMENT									
Subject receives training on usage of autoinjector	X								
Self-administration of investigational product at clinic	X	X			X				
Self-administration of investigational product at home			X	X		X	X		
Study staff dispenses and/or reconciles investigational product		X			X			X	
Amgen investigational product ^e	X	X	X	X	X	X	X		Autoinjectors

Page 3 of 3

BP = blood pressure; DBTP = double-blind treatment period; eDiary = electronic diary; EOS = end of study; ET = early termination; HIT-6 = Headache Impact Test-6; HR = heart rate; **IRT = Interactive Response Technology**; MFIQ = Migraine Functional Impact Questionnaire; MIDAS = Migraine Disability Assessment; MPFID = Migraine Physical Function Impact Diary; OLTP = open-label treatment period; RR = respiratory rate

^a A subject who discontinues investigational product during the OLTP or who completes the study will perform the week 52/EOS visit assessments. Subjects who early terminate will complete the assessments approximately 28 (+3) days after the last dose of investigational product.

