12.2 Appendix 2. Clinical Laboratory Tests

The tests detailed in [Table 12-1](#) will be performed by the central laboratory, except urine pregnancy testing. **During the Baseline period and through the DBTP, hematology and chemistry testing will be at the discretion of the investigator, as well as chemistry testing during the OLTP.**

Local laboratory results are only required in the event that the central laboratory results are not available in time for either study treatment administration and/or response evaluation. If a local sample is required, it is important that the sample for central analysis is obtained at the same time. Additionally, if the local laboratory results are used to make either a study treatment decision or response evaluation, the results must be entered into the **case report form (CRF)**.

Protocol-specific requirements for inclusion or exclusion of subjects are detailed in [Sections 6.1](#) to [6.4](#) of the protocol.

Additional tests may be performed at any time during the study as determined necessary by the investigator or required by local regulations.

Table 12-1. Analyte Listing

Central Laboratory: Chemistry ^a	Central Laboratory: Hematology ^b	Other Labs ^c
Sodium	RBC	Central Laboratory:
Potassium	Hemoglobin	Urine drug screening
Chloride	Hematocrit	Pharmacogenetic studies (optional)
Bicarbonate	MCV	Biomarker development
Total protein	MCH	Hep B surface antigen
Calcium	MCHC	Total Hep B core antibody
Adjusted calcium	RDW	Hep C antibody
Magnesium	Reticulocytes	HIV
Phosphorus	Platelets	
Glucose	WBC	
BUN or Urea	Differential	
Creatinine	• Neutrophils	Local Laboratory:
Uric acid	• Eosinophils	Pregnancy testing-urine
LDH	• Basophils	
Cholesterol ^d	• Lymphocytes	
HDL ^d	• Monocytes	
LDL ^d		
Triglycerides		
Total bilirubin		

Approved

Central Laboratory: Chemistry ^a	Central Laboratory: Hematology ^b	Other Labs ^c
Direct bilirubin		
ALP		
AST (SGOT)		
ALT (SGPT)		
Albumin		

Footnotes defined on next page

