- Wilson's disease and hemochromatosis
- Nonalcoholic fatty liver disease including steatohepatitis
- Nonhepatic causes (eg, rhabdomyolysis, hemolysis)

Approved

If investigational product(s) is/are withheld, the subject is to be followed for possible drug induced liver injury (DILI) according to recommendations in the last section of this appendix.

Rechallenge may be considered if an alternative cause for impaired liver tests (ALT, AST, ALP) and/or elevated TBL, is discovered and the laboratory abnormalities resolve to normal or baseline (see next section in this appendix).

Table 12-2. Conditions for Withholding and/or Permanent Discontinuation of Amgen Investigational Product and Other Protocol-required Therapies Due to Potential Hepatotoxicity

Analyte	Temporary Withholding	Permanent Discontinuation
TBL	> 2x ULN at any time	> 3x ULN
		OR
INR	--	> 1.5x (for subjects not on anticoagulation therapy)
	OR	AND
AST/ALT	> 8x ULN at any time > 5x ULN but < 8x ULN for ≥ 2 weeks > 5x ULN but < 8x ULN and unable to adhere to enhanced monitoring schedule > 3x ULN with clinical signs or symptoms that are consistent with hepatitis (such as right upper quadrant pain/tenderness, fever, nausea, vomiting, and jaundice)	In the presence of no important alternative causes for elevated AST/ALT and/or TBL values > 3x ULN (when baseline was < ULN)
	OR	
ALP	> 8x ULN at any time	--

ALP = alkaline phosphatase; ALT = alanine aminotransferase; AST = aspartate aminotransferase; TBL = total bilirubin; ULN = upper limit of normal

Criteria for Rechallenge of Amgen Investigational Product and Other Protocol-required Therapies After Potential Hepatotoxicity

The decision to rechallenge the subject is to be discussed and agreed upon unanimously by the subject, investigator, and Amgen.

If signs or symptoms recur with rechallenge, then Amgen investigational product is to be permanently discontinued. Subjects who clearly meet the criteria for permanent discontinuation (as described in [Table 12-2](#)) are never to be rechallenged.

Approved

Drug-induced Liver Injury Reporting and Additional Assessments

Reporting

To facilitate appropriate monitoring for signals of DILI, cases of concurrent AST or ALT and TBL and/or INR elevation, according to the criteria specified in the above, require the following:

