- The event is to be reported to Amgen as a serious adverse event within 24 hours of discovery or notification of the event (ie, before additional etiologic investigations have been concluded)
- The appropriate Case Report Form (CRF) (eg, Event CRF) that captures information necessary to facilitate the evaluation of treatment-emergent liver abnormalities is to be completed and sent to Amgen

Other events of hepatotoxicity and potential DILI are to be reported as serious adverse events if they meet the criteria for a serious adverse event defined in [Section 12.4](#).

Additional Clinical Assessments and Observation

All subjects in whom investigational product(s) or protocol-required therapies is/are withheld (either permanently or conditionally) due to potential DILI as specified in [Table 12-2](#) or who experience AST or ALT elevations > 3 x upper limit of normal (ULN) or 2-fold increases above baseline values for subjects with elevated values before drug are to undergo a period of “close observation” until abnormalities return to normal or to the subject’s baseline levels.

Assessments that are to be performed during this period include:

- Repeat AST, ALT, ALP, BIL (total and direct), and INR within 24 hours
- In cases of TBL > 2 x ULN or INR > 1.5 , retesting of liver tests, BIL (total and direct), and INR is to be performed every 24 hours until laboratory abnormalities improve

Testing frequency of the above laboratory tests may decrease if the abnormalities stabilize or the investigational product(s) or protocol-required therapies has/have been discontinued AND the subject is asymptomatic.

Approved

Initiate investigation of alternative causes for elevated AST or ALT and/or elevated TBL.

The following are to be considered depending on the clinical situation:

- Complete blood count with differential to assess for eosinophilia
- Serum total immunoglobulin G (IgG), anti-nuclear antibody anti-smooth muscle antibody, and liver kidney microsomal antibody-1 to assess for autoimmune hepatitis
- Serum acetaminophen (paracetamol) levels
- A more detailed history of:
 - Prior and/or concurrent diseases or illness
 - Exposure to environmental and/or industrial chemical agents
 - Symptoms (if applicable) including right upper quadrant pain, hypersensitivity-type reactions, fatigue, nausea, vomiting, and fever
 - Prior and/or concurrent use of alcohol, recreational drugs and special diets

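### Protocol 10.4.2.3.3 omits laboratory analysis because tests are done only at screening; the schedules contradict this, and post-dose liver values have no planned summary or listing

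*Protocol*

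**What the plan says.** Protocol 10.4.2.3.3 declares laboratory analysis not applicable on one ground: "laboratory measurements are only to be performed at screening".

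Other parts of the protocol provide for later testing:

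- **Table 2-1 (double-blind period).** Chemistry: "After screening, chemistry testing will be at the discretion of the investigator". Hematology: "After screening, hematology testing will be at the discretion of the investigator". Both are done centrally.
- **Table 2-2 (open-label period).** The chemistry row reads "X (to be performed at the discretion of the investigator" and, as extracted, carries a further mark under week 52/EOS.
- **Appendix 2.** For the baseline and double-blind periods, "hematology and chemistry testing will be at the discretion of the investigator, as well as chemistry testing during the OLTP". Footnote a of Table 12-1 agrees.
- **Appendix 7, Table 12-2.** Withholding and discontinuation conditions are set on total bilirubin, INR, AST/ALT and ALP, for example "> 5x ULN but < 8x ULN for ≥ 2 weeks".

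The safety endpoints in SAP 2.1 are adverse events and vital signs. SAP 9.6 covers adverse events, vital signs, exposure and concomitant medication. SAP Section 12 lists the data with no planned analysis and names only biomarker and interview-substudy data.

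**The concern.** A section that omits an analysis because the data do not exist should be right about that. Here the protocol lets the data exist, and it attaches decisions about study drug to the same analytes. The SAP then neither analyses the values nor says that they will be left unanalysed.

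At stake is a small but concrete part of the safety record. Post-dose liver values held in the central laboratory data would reach the study report only when someone turned them into an event or a treatment decision. A reader of the report could not tell how many subjects were tested after dosing, how many crossed a Table 12-2 threshold, in which arm, or how high the values went.

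**Working it through.** No alpha, power or rate is involved, so the check is a side-by-side reading.

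**Step 1. Is the stated reason true?**

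| Source | Post-screening laboratory testing |
|---|---|
| Protocol 10.4.2.3.3 | None |
| Table 2-1, chemistry and hematology | Discretionary through the double-blind period, central laboratory |
| Table 2-1, urine drug testing | Scheduled at every double-blind visit, central laboratory |
| Table 2-2, chemistry | Discretionary, plus a separate mark |
| Appendix 2 and Table 12-1 footnotes | Chemistry discretionary in baseline, double-blind and open-label periods; hematology in baseline and double-blind periods |

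The reason is contradicted by both schedules and by Appendix 2.

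**Step 2. Where does the extra mark in Table 2-2 fall?** The table has eight visit columns: weeks 24, 28, 32, 36, 40, 44, 48 and 52/EOS. In the extracted chemistry row the discretionary entry sits in column 1 and the further mark seven cells later, so 1 + 7 = column 8, which is week 52/EOS. The urine drug test row directly above has the same discretionary entry and no such mark. That suggests a real entry, but the position should be checked against the original table because the text was extracted from PDF. Appendix 2 gives no fixed week 52 test, so the two places disagree.

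**Step 3. Is any output planned for the values?** SAP 9.6 has no laboratory summary or listing. None of the events of interest in SAP 9.6.2 is hepatic. SAP 5.4.1 assigns efficacy assessments, vital signs, adverse events and concomitant medications to treatment periods, but not laboratory data.

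**Step 4. By what routes would a hepatic abnormality still appear?**

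- Clinically relevant changes are recorded on the Event CRF (Protocol 9.2.4), and treatment-emergent events are tabulated (Protocol 10.4.2.3.2, SAP 9.6.2).
- AST or ALT elevation concurrent with bilirubin and/or INR elevation is reported as a serious adverse event within 24 hours, and laboratory results for a potential liver-injury event go into the CRFs (Appendix 7).
- Reasons for stopping study drug are tabulated (SAP 9.2), as are dose changes and their reasons (SAP 9.6.4).

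**Step 5. What do those routes miss?** Protocol 9.2.4 says that abnormal results without clinical significance are in general not recorded as adverse events. The automatic serious-event rule covers concurrent elevations, whereas Table 12-2 also has withholding conditions on bilirubin alone, AST/ALT alone and ALP alone. Event tables by preferred term do not show values, peaks or the number of subjects tested.

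**Step 6. INR.** Appendix 7 uses INR in the Table 12-2 conditions and in the follow-up work-up ("Repeat AST, ALT, ALP, BIL (total and direct), and INR within 24 hours"). Table 12-1 does not list it. Appendix 2 does allow additional tests at any time, so this is a gap to clarify.

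**The case against.** The strongest reply is that the omission is deliberate and the wording merely loose. No chemistry sample is required in the double-blind period, so the sentence may mean that tests are required only at screening. The current safety endpoints are adverse events and vital signs, the SAP matches them, and the Amendment 2 log shows laboratory values being taken out of the safety endpoints. On that view, adding laboratory output is a preference. Much of this stands: no planned endpoint lacks an analysis, and reduced monitoring is the sponsor's choice. But the text does not say that the values will be left out by choice; it says that there are none. SAP Section 12, where such a choice would be declared, is silent.

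Three stronger readings are tempting, and the documents do not support them.

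- A reader might infer that collected hepatic data would never be reported. The routes in Step 4 of the working show otherwise.
- A reader might infer that every open-label subject has a week 52 result that goes untabulated. That rests on one mark in an extracted table, and Appendix 2 calls open-label chemistry discretionary.
- A reader might infer that the Appendix 7 rules contradict discretionary testing. Those rules act on abnormal values once found and then prescribe repeat tests, so the two can coexist.

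It is also fair to object to shift or worst-value tables by arm. Double-blind samples are triggered by investigators, and at week 52 all open-label subjects are on erenumab.

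**Conclusion.** The point holds in a limited form. The reason given in Protocol 10.4.2.3.3 is wrong on the protocol's own schedules, and any post-dose laboratory values would be neither summarised nor listed. The loss is confined to elevations judged not clinically significant and to a by-arm view of values among subjects tested.

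The size cannot be derived. In the double-blind period it depends on how often investigators order tests, which could be never. In the open-label period it depends on whether the week 52 mark is a scheduled test: if so, most subjects reaching that visit would have a value; if not, the number is again a matter of discretion. The efficacy analyses are not affected.

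The conclusion assumes that the extracted Table 2-2 is faithful only as regards the week 52 mark. The contradiction with Table 2-1 and Appendix 2 does not depend on it.

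**What to change.** 1. **Correct the reason** in Protocol 10.4.2.3.3, or record the correction in SAP Section 10, so that it reflects discretionary post-screening testing.
2. **Reconcile** the Table 2-2 week 52 chemistry entry with Appendix 2 and Table 12-1, and state where INR is measured and recorded, given its use in Appendix 7. Which clinical rule applies is for the sponsor to decide; this review prescribes none.
3. **Add to SAP 9.6** a listing of post-screening ALT, AST, ALP and total bilirubin. Add counts of subjects meeting the Table 12-2 laboratory thresholds, by treatment and period, with subjects tested as the denominator. SAP 5.4.1 needs a period rule for laboratory data; the one for vital signs could serve. Mark conditions that also need symptoms, serial values or exclusion of other causes, since a single sample cannot settle them.
4. **State the limits** with the output: discretionary sampling is selective, and open-label data have no placebo comparator.
5. **Add a screening-to-week-52 shift table** only if the week 52 test is confirmed as scheduled.

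If the sponsor prefers no laboratory output, the minimum is to say so in SAP Section 12.

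The cost is protocol or SAP wording and a small amount of extra output on data already held. The downside is that the counts could be over-read without the selection caveat.
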